Annex I

Diagnosis and operation codes.

The list of diagnosis and operation codes will be provided in separate documents.

- Annex 1.1 - Diagnosis and operation codes for CPRD Gold

Annex 1.1.zip

- Annex 1.2 - Diagnosis and operation codes for CPRD Aurum

Annex 1.2.zip

- Annex 1.3 - Diagnosis and operation codes for Finland and Sweden

Annex 1.3.xlsx

Annex II

ATC codes used to define treatments

The corresponding READ codes used to define treatments for CPRD will be provided in a separate document.

- Annex 2.1 - READ codes for treatment definition for CPRD Gold

- Annex 2.2 - READ codes for treatment definition for CPRD Aurum

Proprietary confidential information © 2024 Boehringer Ingelheim International GmbH or one or more of its affiliated companies

Drug Group	ATC codes
Empagliflozin alone or in combination with metformin; excluding fixed dose combinations with drugs other than empagliflozin	
Empagliflozin	A10BK03 (previously A10BX12)
metformin and empagliflozin	A10BD20
Other SGLT-2 inhibitors; excluding empagliflozin and excluding fixed-dose combinations with DPP-4 inhibitors	
Dapagliflozin	A10BK01 (previously: A10BX09)
Canagliflozin	A10BK02 (previously: A10BX11)
Ertugliflozin	A10BK04
Ipragliflozin	A10BK05
metformin and dapagliflozin	A10BD15
metformin and canagliflozin	A10BD16
Metformin and ertugliflozin	A10BD23
DPP-4 inhibitors; excluding fixed-dose combinations with SGLT-2 inhibitors	
Sitagliptin	A10BH01
Vildagliptin	A10BH02
Saxagliptin	A10BH03
Alogliptin	A10BH04
Linagliptin	A10BH05
Evogliptin	A10BH07
Gemigliptin	A10BH06
sitagliptin and simvastatin	A10BH51
gemigliptin and rosuvastatin	A10BH52
metformin and sitagliptin	A10BD07
metformin and vildagliptin	A10BD08
pioglitazone and alogliptin	A10BD09
metformin and saxagliptin	A10BD10
metformin and linagliptin	A10BD11
pioglitazone and sitagliptin	A10BD12
metformin and alogliptin	A10BD13
metformin and gemigliptin	A10BD18
metformin and evogliptin	A10BD22
Fixed dose combinations of SGLT-2 inhibitors with DPP-4 inhibitors	
linagliptin and empagliflozin	A10BD19
saxagliptin and dapagliflozin	A10BD21
Sitagliptin and ertugliflozin	A10BD24
metformin, saxagliptin and dapagliflozin	A10BD25
Insulin	
Insulins and analogues	A10A
Metformin (alone or in fixed dose combinations)	
Metformin	A10BA02
metformin and sulfonylureas	A10BD02
metformin and rosiglitazone	A10BD03
metformin and pioglitazone	A10BD05
metformin and sitagliptin	A10BD07
metformin and vildagliptin	A10BD08

Proprietary confidential information © 2024 Boehringer Ingelheim International GmbH or one or more of its affiliated companies

[figure not shown]
metformin and saxagliptin	A10BD10
metformin and linagliptin	A10BD11
metformin and alogliptin	A10BD13
metformin and repaglinide	A10BD14
metformin and dapagliflozin	A10BD15
metformin and canagliflozin	A10BD16
metformin and acarbose	A10BD17
metformin and gemigliptin	A10BD18
metformin and empagliflozin	A10BD20
metformin and evogliptin	A10BD22
metformin and ertugliflozin	A10BD23
metformin, saxagliptin and dapagliflozin	A10BD25
Other glucose lowering medication	
exenatide	A10BX04
liraglutide	A10BX07
lixisenatide	A10BX10
albiglutide	A10BX13
repaglinide	A10BX02
nateglinide	A10BX03
mitiglinide	A10BX08
metformin and repaglinide	A10BD14
pramlintide	A10BX05
benfluorex	A10BX06
guar gum	A10BX01
GLP-1 drugs	
Glucagon-like peptide-1 receptor (GLP-1) analogues	A10BJ
Thiazolidinediones	
Thiazolidinediones	A10BG
glimepiride and rosiglitazone	A10BD04
metformin and rosiglitazone	A10BD03
glimepiride and pioglitazone	A10BD06
metformin and pioglitazone	A10BD05
pioglitazone and alogliptin	A10BD09
pioglitazone and sitagliptin	A10BD12
Sulfonylureas	
Sulfonylureas	A10BB
phenformin and sulfonylureas	A10BD01
metformin and sulfonylureas	A10BD02
glimepiride and rosiglitazone	A10BD04
glimepiride and pioglitazone	A10BD06
glymidine	A10BC01
tolbutamide	V04CA01
Antihypertensives/diuretics	
Antihypertensives	C02
Diuretics	C03
Beta blocking agents	C07
Calcium channel blockers	C08
Agents acting on the renin-angiotensin system	C09
minoxidil	D11AX01
clonidine	N02CX02
clonidine	S01EA04

Proprietary confidential information © 2024 Boehringer Ingelheim International GmbH or one or more of its affiliated companies

guanethidine	S01EX01
theobromin	R03DA07
theobromine, combinations	R03DA57
diazoxide	V03AH01
Non-steroidal anti-inflammatory drugs (NSAIDs)	
Antiinflammatory and antirheumatic products, non-steroids	M01A
Oral steroids	
Corticosteroids for systemic use, plain	H02A
Corticosteroids for systemic use, combinations	H02B
Statins, fibrates	
HMG CoA reductase inhibitors	C10AA
Fibrates	C10AB
HMG CoA reductase inhibitors in combination with other lipid modifying agents	C10BA
HMG CoA reductase inhibitors, other combinations	C10BX
sitagliptin and simvastatin	A10BH51
Lipid modifying agents	
Lipid modifying agents	C10
sitagliptin and simvastatin	A10BH51
nicotinic acid	C04AC01
nicotinyl alcohol (pyridylcarbinol)	C04AC02
Zoledronic acid	
Zoledronic acid	M05BA08
zoledronic acid, calcium and colecalciferol, sequential	M05BB08
Antibiotics	
Antibacterials for systemic use	J01

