ANNEX 4. CODES TO IDENTIFY EXPOSURE VARIABLES

No.	Variable	ATC codes ³	Time-dependent (T) / fixed at cohort entry (F)	How the effect of variable is accounted for ¹
1	AT / ITT: Empagliflozin	Empagliflozin A10BK03 (current), A10BX12 (previous)	T / F	E
2	AT / ITT: DPP-4 inhibitor	DPP-4 inhibitors ATC beginning with A10BH Fixed-dose combinations Will be identified from ATC class A10BD	T / F	E
3	AT / ITT, FDCM ² : empagliflozin		T / F	E
4	AT / ITT, FDCM ² : DPP-4 inhibitor		T / F	E
5	Empagliflozin current use		T	E
6	Empagliflozin: cumulative duration of exposure		T	E
7	Empagliflozin: cumulative dosage of exposure		T	E
8	Empagliflozin: time since last dose		T	E
Other OAD treatments				
9	Metformin	ATC beginning with A10BA	T	PS / A / VS, RS, TV, SG
10	Sulphonylureas	ATC beginning with A10BB	T	PS / A / VS, RS, TV

No.	Variable	ATC codes ³	Time-dependent (T) / fixed at cohort entry (F)	How the effect of variable is accounted for ¹
11	Insulin	ATC beginning with A10A	T	PS / A / VS, RS, TV
12	Thiazolidinediones	ATC beginning with A10BG	T	PS / A / VS, RS, TV
13	Alpha glucosidase inhibitors	ATC beginning with A10BF	T	PS / A / VS, RS, TV
14	GLP-1 agonists	Will be identified from ATC classes A10BJ and A10BX	T	PS / A / VS, RS, TV
15	Other blood glucose lowering drugs, excluding insulins	ATC beginning with A10BX that is not included elsewhere		
16	Treatment complexity (mono, dual and triple combination therapy)		T	PS / A / VS, RS, TV
17	Switch or add-on		T	PS / A / VS, RS, TV
Exclusion / Censoring				
18	DPP-4 (Linagliptin) and Empagliflozin	A10BD19	T	Censoring / Exclusion
19	Discontinuation of primary exposure		T	Censoring
20	Switch to other SGLT-2 inhibitor use	A10BK02, A10BX11, A10BK01, A10BX09, A10BK04, A10BD16, A10BD15, A10BD23	T	Censoring / Exclusion

No.	Variable	ATC codes ³	Time-dependent (T) / fixed at cohort entry (F)	How the effect of variable is accounted for ¹
21	Use of fixed-dose combinations of SGLT-2 inhibitors with DPP-4 inhibitors	Identified from ATC class A10BD	T	Censoring / Exclusion

¹ E – Exposure, A – adjusted in the Cox model, VS – potential confounder and will be adjusted for using variable selection, PS – one of the PS matching variable at baseline, TV – time-varying confounder and adjusted for in MSM, RS – defines the risk set in NCC, SG – used as a subgroup in stratified analyses, / - and/or

2 FDCM – Fixed-dose combination with metformin

3 New drugs will be included in the variable definitions if they become available during the study period.

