5.3.3. Concomitant medications

Table 14 Other diabetic medication exposure definitions

Exposure	Definition	Details	Data source
Concomitant use of insulin at index date	Variable indicating the concomitant use of insulin with study drugs at index date, using data within the 180-day period prior to index date. ATC codes for insulins in Annex II. Evaluated at index using data within the 180-day period prior to index date.	Time-fixed Categorical: Yes No	UK: CPRD Sweden: SPDR Finland: FPR
Ever exposed to insulin	Variable indicating any use of insulin using data from 180 days prior to index date onwards. ATC codes for insulins in Annex II. Updating from 180 days prior to index date onwards.	Time-dependent Categorical: Yes No	UK: CPRD Sweden: SPDR Finland: FPR
Metformin exposure	Time updating current exposure status to metformin based on purchased amounts and daily defined or prescribed dose, using data from 180 days prior to index date onwards. ATC codes for metformin in Annex II. Updating from 180 days prior to index date onwards.	Time-dependent Categorical: Yes No	UK: CPRD Sweden: SPDR Finland: FPR
Ever exposed to metformin	Variable indicating any use of metformin using data from 180 days prior to index date onwards. ATC codes for metformin in Annex II. Updating from 180 days prior to index date onwards.	Time-dependent Categorical: Yes No	UK: CPRD Sweden: SPDR Finland: FPR
Ever exposed to GLP-1 drugs	Variable indicating any use of GLP-1 drugs using data from 180 days prior to index date onwards. ATC codes for GLP-1 drugs in Annex II. Updating from 180 days prior to index date onwards.	Time-dependent Categorical: Yes No	UK: CPRD Sweden: SPDR Finland: FPR

Proprietary confidential information © 2024 Boehringer Ingelheim International GmbH or one or more of its affiliated companies

Ever exposed to thiazolidinedi ones	Variable indicating any use of thiazolidinediones using data from 180 days prior to index date onwards.	Time-dependent Categorical: Yes No	UK: CPRD Sweden: SPDR Finland: FPR
	ATC codes for thiazolidinediones in Annex II.		
Updating from 180 days prior to index date onwards.			
Ever exposed to sulfonylureas	Variable indicating any use of sulfonylureas using data from 180 days prior to index date onwards.	Time-dependent Categorical: Yes No	UK: CPRD Sweden: SPDR Finland: FPR
	ATC codes for sulfonylureas in Annex II.		
Updating from 180 days prior to index date onwards.			

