Ever exposed to other glucose lowering medication	Variable indicating any use of oral glucose lowering drugs other than the study drugs using data from 180 days prior to index date onwards.	Time-dependent Categorical: Yes No	UK: CPRD Sweden: SPDR Finland: FPR
	ATC codes for other glucose lowering drugs in Annex II.		
Updating from 180 days prior to index date onwards.			
Treatment complexity at index	Treatment complexity at index date is categorized by the number of drug classes in concomitant use including study drugs, using data from 180 days prior to index date onwards.	Time-fixed Categorical: Monotherapy Dual combination therapy Triple combination therapy or higher	UK: CPRD Sweden: SPDR Finland: FPR
	Evaluated at index using data from 180 days prior to index date onwards.		

Table 15 Other non-diabetic concomitant medication use variables

Variable	Definition	Details	Data source
Antihypertensive s/diuretics exposure at index date	Exposure status at index date of any antihypertensives/diuretics (including combinations) based on purchased amounts and daily defined dose using data within 180-day period prior to index date. ATC codes for antihypertensives/diuretics in Annex II. Evaluated at index date using data within 180-day period prior to index date.	Time-fixed Categorical: Yes No	UK: CPRD Sweden: SPDR Finland: FPR
Non-steroidal anti-inflammatory drugs (NSAIDs) exposure at index date	Exposure status at index date of any NSAID (including combinations) based on purchased amounts and daily defined dose using data within 180-day period prior to index date. ATC codes for NSAID in Annex II. Evaluated at index date using data within 180-day period prior to index date.	Time-fixed Categorical: Yes No	UK: CPRD Sweden: SPDR Finland: FPR
Oral steroids exposure at index date	Exposure status at index date of any oral steroid (including combinations) based on purchased amounts and daily defined dose using data within 180-day period prior to index date. ATC codes for oral steroids in Annex II. Evaluated at index date using data within 180-day period prior to index date.	Time-fixed Categorical: Yes No	UK: CPRD Sweden: SPDR Finland: FPR

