6.7.2. Comparative analysis

Hazard ratios (HRs) for the outcomes defined in Table 8 will be estimated for PS matched cohorts using Cox's PH model with time-varying covariates, if model pre-requisites are fulfilled. HRs will be presented along with 95% CIs. Proportional hazards assumptions for time-fixed exposure variables will be assessed for each model by plotting scaled Schoenfeld residuals.

The comparative analyses will be performed separately for the matched full cohort and matched metformin-user cohort.

Crude model

Crude HRs are calculated using a Cox PH model with as-treated exposure (as defined in Section 5.1.7) as the only included variable.

HRs estimated using the crude model will be presented along with 95% CIs. A table template for the result is given in Table 23. Analysis will be performed separately for each country.

Crude HRs with 95% CIs will be collected from all study countries to carry out meta-analyses as described in Section 6.7.3.2. Results will be reported as in Figure 8.

Base model

Based on the crude model, the base model will be further adjusted with the unbalanced covariates at index date (standard difference $\geq 10\%$) among the variables included in the propensity score model (Section 6.6). The inclusion of adjusting variables will be considered based on data availability as described in Section 10.

HRs estimated using the base model will be presented along with 95% CIs. A table template for the result is given in Table 24. Analysis will be performed separately for each country. HRs with 95% CIs estimated using base model will be collected from all study countries to carry out meta-analyses as described in Section 6.7.3.2. Results will be reported as in Figure 8.

Adjusted model

The base model will be further adjusted with selected time-dependent variables. The following time-dependent variables will be initially considered for inclusion (as detailed in Section 9) in the adjusted Cox's PH model:

- HbA1c value (as defined in Table 11)
- Kidney or genitourinary stones (as defined in Table 13)
- UTI or pyelonephritis (as defined in Table 13)
- Ever exposed to insulin (as defined in Table 14)
- Ever exposed to metformin (as defined in Table 14)

Proprietary confidential information © 2024 Boehringer Ingelheim International GmbH or one or more of its affiliated companies

- Ever exposed to other glucose lowering medication (as defined in Table 14)
- Ever exposed to GLP-1 drugs (as defined in Table 14)

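### SAP Annex II puts four GLP-1 agonists with A10BX codes in the other-drug group, against protocol Annex 4, so two covariates can be miscoded in Sweden and Finland

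*SAP*

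**What the plan says.** Protocol Annex 4, row 14, on GLP-1 agonists: "Will be identified from ATC classes A10BJ and A10BX". Row 15 leaves the other blood glucose lowering drugs (excluding insulins) as a residual: "ATC beginning with A10BX that is not included elsewhere".

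SAP Annex II has one line under GLP-1 drugs, "Glucagon-like peptide-1 receptor (GLP-1) analogues", with code A10BJ and no A10BX code. Exenatide, liraglutide, lixisenatide and albiglutide are listed by name, with their A10BX codes, under "Other glucose lowering medication".

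SAP Table 14 (section 5.3.3) builds two yes/no covariates from these groups and refers to Annex II for the codes. The first is "Variable indicating any use of GLP-1 drugs using data from 180 days prior to index date onwards". The second is worded as "Variable indicating any use of oral glucose lowering drugs other than the study drugs", over the same window. SAP section 6.7.2 names both among the time-dependent variables to be considered for the adjusted model, the first as "Ever exposed to GLP-1 drugs (as defined in Table 14"). Sections 6.5.1 and 6.6.2 take the Table 14 variables, at index-date status, into the list considered for the propensity score and into the balance assessment.

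**The concern.** The two documents give opposite instructions for the same records, and the SAP is the one a programmer will follow. It looks like an oversight, for three reasons. The SAP change log (section 3) has no entry on GLP-1 codes. Table 14 words the other-drug variable as oral drugs, and the table shells report oral glucose-lowering use and GLP-1 use as separate rows. For the SGLT-2 inhibitors the same annex keeps former A10BX codes beside the current code in the correct group, for example "A10BK03 (previously A10BX12"), so the plan expects former codes in the data.

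What is at stake is confounder control. Protocol section 8.1 describes GLP-1 analogues in dual therapy as having a restricted target population, so their use says something about which patients are channelled to which drug. Three rules in the SAP also act on the coded values:

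- the base model adjusts for a variable only if its standardized difference is at least 10%;
- a covariate needs at least 5 outcome events per category to enter a Cox model;
- if a model fails to converge, covariates are dropped in order of standardized difference, smallest first.

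Splitting GLP-1 users between two variables can change the result of each rule.

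**Working it through.** No sample-size or power figure is involved, so the check compares code lists and then asks what can be said about size.

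**Step 1. Run each code through both rules.** That the four substances are GLP-1 agonists is general drug-class knowledge. It agrees with the protocol's statement that GLP-1 agonists occur in A10BX.

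| Substance | Code in SAP Annex II | Protocol Annex 4 | SAP Annex II |
|---|---|---|---|
| Exenatide | A10BX04 | GLP-1 Yes, other No | GLP-1 No, other Yes |
| Liraglutide | A10BX07 | GLP-1 Yes, other No | GLP-1 No, other Yes |
| Lixisenatide | A10BX10 | GLP-1 Yes, other No | GLP-1 No, other Yes |
| Albiglutide | A10BX13 | GLP-1 Yes, other No | GLP-1 No, other Yes |

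All 4 of 4 codes are classified in opposite ways. The same substance recorded under A10BJ is GLP-1 Yes under both documents.

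**Step 2. Apply the Table 14 window.** Both covariates use data from 180 days before index onwards, so older history enters neither. A patient is wrong on both variables only while GLP-1 use in that window has been recorded solely under A10BX. The first A10BJ record turns the GLP-1 variable to Yes from that date. The other-drug variable stays Yes.

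**Step 3. Where it applies.** Sweden and Finland use the ATC list directly. For the UK, Annex II refers to separate code lists (Annexes 2.1 and 2.2), which are not shown.

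**Step 4. Size.** The documents do not say when GLP-1 records moved from A10BX to A10BJ, whether past records were recoded, or how many cohort members use GLP-1 drugs. If all history was recoded, none are affected. Otherwise, suppose A10BX recording of GLP-1 drugs ended at the close of year y (an assumption). An affected patient must then have an index date no later than 180 days after that. Protocol Table 6 gives empagliflozin initiators by year:

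- Sweden plus Finland, 2014 and 2015: 0 + 0 + 629 + 91 = 720
- through 2016: 720 + 2,181 + 2,201 = 5,102
- through 2017: 5,102 + 4,811 + 3,725 = 13,638
- through 2018: 13,638 + 8,738 + 4,293 = 26,669
- total: 32,334 + 18,269 = 50,603

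| Assumed end of A10BX recording | Indexed by then | Share of 50,603 |
|---|---|---|
| close of 2015 | 720 | 1.4% |
| close of 2016 | 5,102 | 10.1% |
| close of 2017 | 13,638 | 27.0% |

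The 180-day window adds part of the following year, so each count is a little low but stays below the next cumulative count (for 2017, below 26,669, or 52.7%). These are pools of initiators within which affected patients would lie. They are not counts of affected patients: only GLP-1 users in the pool with no A10BJ record in the relevant time are miscoded.

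**The case against.** The strongest case on the other side accepts the code conflict and disputes its consequence.

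- **Calendar time is largely matched.** SAP section 6.5.2 requires comparators to start within 90 days of the empagliflozin initiator, section 6.3 describes index year as an exact matching criterion, and calendar year is a propensity-score candidate. Matched patients mostly share a coding era, so the error should be similar in both arms. This stands, except that section 6.5.2 allows the time criterion to be relaxed.
- **The information is merged, not lost.** A miscoded user is still Yes on a variable considered for the propensity score, beside insulin use, treatment complexity and duration of treated diabetes. This stands in part: the other-drug group also holds repaglinide, nateglinide and other drugs, so it is a poorer marker.
- **The variables may not enter the models.** The SAP only considers them for the propensity score and the adjusted Cox model. A reader might infer that both are certain to be in the adjusted model; section 6.7.2 does not say that.
- **Registers may hold recoded history.** This is possible. The documents are silent, and the SGLT-2 rows show that the plan did not rely on it for those drugs.

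A reader might also take the row of protocol Table 2 for other non-insulin drugs (15,151 in Sweden, 9,088 in the UK) as an upper bound on the number affected. It is not one. Those are all database users of a mixed category in 2014 (Sweden) or January 2014 to July 2015 (UK). They are not eligible cohort members, and they do not cap later years. Table 6 shows 0 empagliflozin and 3,214 DPP-4 initiators in Sweden in 2014. The UK figure also concerns a country whose code lists are not shown.

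**Conclusion.** The conflict is real and should be corrected before programming. The SAP contradicts protocol Annex 4, its own description of the other-drug variable, and its own handling of former SGLT-2 codes. The SAP cites protocol version 6.0 and the protocol reviewed is version 8.0, but the amendment entries for 7.0 and 8.0 mention no change to GLP-1 codes.

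The confirmed consequence is limited to two covariates in Sweden and Finland, for use seen only under A10BX inside the Table 14 window. They feed the propensity score if selected, the balance tables, the stratified incidence rates and, if retained, the adjusted Cox model. The number affected is unknown and may be zero. The effect on the hazard ratio is unknown and probably small, and the documents give no ground for expecting a particular direction. Nor do they support a claim that the CPRD lists carry the same fault; those can only be checked.

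**What to change.** In SAP Annex II, define GLP-1 drugs as A10BJ plus every GLP-1 agonist coded in A10BX, which means at least A10BX04, A10BX07, A10BX10 and A10BX13. Remove those codes from the other glucose-lowering group. Search the Swedish and Finnish extracts for any further A10BX code that belongs to a GLP-1 agonist, since the protocol rule is not confined to these four. Check Annexes 2.1 and 2.2 for the same grouping, and record the change in SAP section 3.

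The cost is four code rows moved, one search of the extracts and one check of the CPRD lists. No new data are needed. If the covariates have already been built, the two variables must be rebuilt and the propensity score, matching and models that use them rerun.

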Annex III

Tables and figures templates

Abbreviations: DPP-4, dipeptidyl peptidase-4; T2DM, Type 2 diabetes mellitus.

Definitions: Index date, the date of first purchase/prescription of empagliflozin or DPP-4 between August 1, 2014 and June 30, 2020.

Proprietary confidential information © 2024 Boehringer Ingelheim International GmbH or one or more of its affiliated companies

Table 17 Patients baseline characteristics in each of the study groups and in the total study population in [Study country].

	Empagliflozin at index date	DPP-4 inhibitors at index date	[Country] Study population (Total)
	N	N	
Age at index (years)			
18-49	N (x.xx%)	N (x.xx%)	N (x.xx%)
50-64	N (x.xx%)	N (x.xx%)	N (x.xx%)
65-69	N (x.xx%)	N (x.xx%)	N (x.xx%)
70-74	N (x.xx%)	N (x.xx%)	N (x.xx%)
75-79	N (x.xx%)	N (x.xx%)	N (x.xx%)
80-84	N (x.xx%)	N (x.xx%)	N (x.xx%)
85 and over	N (x.xx%)	N (x.xx%)	N (x.xx%)
Range (min,max)	(min, max)	(min, max)	(min, max)
mean (± sd)	mean (± sd)	mean (± sd)	mean (± sd)
median (Q1,Q3)	median (Q1,Q3)	median (Q1,Q3)	median (Q1,Q3)
Sex			
Male	N (x.xx%)	N (x.xx%)	N (x.xx%)
Female	N (x.xx%)	N (x.xx%)	N (x.xx%)
Highest level of education			
Compulsory	N (x.xx%)	N (x.xx%)	N (x.xx%)
Upper secondary	N (x.xx%)	N (x.xx%)	N (x.xx%)
Post secondary	N (x.xx%)	N (x.xx%)	N (x.xx%)
Disposable income, Individual			
< Q1	N (x.xx%)	N (x.xx%)	N (x.xx%)

Proprietary confidential information © 2024 Boehringer Ingelheim International GmbH or one or more of its affiliated companies

	Empagliflozin at index date	DPP-4 inhibitors at index date	[Country] Study population (Total)
	N	N	
Q1 – Q2	N (x.xx%)	N (x.xx%)	N (x.xx%)
Q2 – Q3	N (x.xx%)	N (x.xx%)	N (x.xx%)
≥ Q3	N (x.xx%)	N (x.xx%)	N (x.xx%)
Range (min,max)	(min, max)	(min, max)	(min, max)
mean (± sd)	mean (± sd)	mean (± sd)	mean (± sd)
median (Q1,Q3)	median (Q1,Q3)	median (Q1,Q3)	median (Q1,Q3)
Disposable income, family			
< Q1	N (x.xx%)	N (x.xx%)	N (x.xx%)
Q1 – Q2	N (x.xx%)	N (x.xx%)	N (x.xx%)
Q2 – Q3	N (x.xx%)	N (x.xx%)	N (x.xx%)
≥ Q3	N (x.xx%)	N (x.xx%)	N (x.xx%)
Range (min,max)	(min, max)	(min, max)	(min, max)
mean (± sd)	mean (± sd)	mean (± sd)	mean (± sd)
median (Q1,Q3)	median (Q1,Q3)	median (Q1,Q3)	median (Q1,Q3)
Marital status			
Registered partnership (incl. married)	N (x.xx%)	N (x.xx%)	N (x.xx%)
Widowed	N (x.xx%)	N (x.xx%)	N (x.xx%)
Separated	N (x.xx%)	N (x.xx%)	N (x.xx%)
Single	N (x.xx%)	N (x.xx%)	N (x.xx%)
Calendar year of index date			
2014	N (x.xx%)	N (x.xx%)	N (x.xx%)
2015	N (x.xx%)	N (x.xx%)	N (x.xx%)
2016	N (x.xx%)	N (x.xx%)	N (x.xx%)

Proprietary confidential information © 2024 Boehringer Ingelheim International GmbH or one or more of its affiliated companies

	Empagliflozin at index date	DPP-4 inhibitors at index date	[Country] Study population (Total)
	N	N	
2017	N (x.xx%)	N (x.xx%)	N (x.xx%)
2018	N (x.xx%)	N (x.xx%)	N (x.xx%)
2019	N (x.xx%)	N (x.xx%)	N (x.xx%)
2020	N (x.xx%)	N (x.xx%)	N (x.xx%)
2021	N (x.xx%)	N (x.xx%)	N (x.xx%)
Duration of look-back period			
1	N (x.xx%)	N (x.xx%)	N (x.xx%)
2-5	N (x.xx%)	N (x.xx%)	N (x.xx%)
6-9	N (x.xx%)	N (x.xx%)	N (x.xx%)
10 and over	N (x.xx%)	N (x.xx%)	N (x.xx%)
Range (min,max)	(min, max)	(min, max)	(min, max)
mean (± sd)	mean (± sd)	mean (± sd)	mean (± sd)
median (Q1,Q3)	median (Q1,Q3)	median (Q1,Q3)	median (Q1,Q3)
Time since first diabetes diagnosis at index date			
<Q1	N (x.xx%)	N (x.xx%)	N (x.xx%)
≥ (x<Q2	N (x.xx%)	N (x.xx%)	N (x.xx%)
≥ (x<Q3	N (x.xx%)	N (x.xx%)	N (x.xx%)
≥ (N (x.xx%)	N (x.xx%)	N (x.xx%)
Range (min,max)	(min, max)	(min, max)	(min, max)
mean (± sd)	mean (± sd)	mean (± sd)	mean (± sd)

Proprietary confidential information © 2024 Boehringer Ingelheim International GmbH or one or more of its affiliated companies

	Empagliflozin at index date	DPP-4 inhibitors at index date	[Country] Study population (Total)
	N	N	
median (Q1,Q3)	median (Q1,Q3)	median (Q1,Q3)	median (Q1,Q3)
Duration of treated diabetes at index date			
Range (min,max)	(min, max)	(min, max)	(min, max)
mean (± sd)	mean (± sd)	mean (± sd)	mean (± sd)
median (Q1,Q3)	median (Q1,Q3)	median (Q1,Q3)	median (Q1,Q3)
Diabetes treatment complexity at index date			
Monotherapy	N (x.xx%)	N (x.xx%)	N (x.xx%)
Dual combination therapy	N (x.xx%)	N (x.xx%)	N (x.xx%)
Triple combination therapy	N (x.xx%)	N (x.xx%)	N (x.xx%)
Insulin use prior to index date			
Yes	N (x.xx%)	N (x.xx%)	N (x.xx%)
No	N (x.xx%)	N (x.xx%)	N (x.xx%)
Insulin use at index date			
Yes	N (x.xx%)	N (x.xx%)	N (x.xx%)
No	N (x.xx%)	N (x.xx%)	N (x.xx%)
Metformin use prior to index date			
Yes	N (x.xx%)	N (x.xx%)	N (x.xx%)
No	N (x.xx%)	N (x.xx%)	N (x.xx%)
Metformin use at index date			
Yes	N (x.xx%)	N (x.xx%)	N (x.xx%)

Proprietary confidential information © 2024 Boehringer Ingelheim International GmbH or one or more of its affiliated companies

	Empagliflozin at index date	DPP-4 inhibitors at index date	[Country] Study population (Total)
	N	N	
No	N (x.xx%)	N (x.xx%)	N (x.xx%)
Oral glucose lowering drugs use prior to index date			
Yes	N (x.xx%)	N (x.xx%)	N (x.xx%)
No	N (x.xx%)	N (x.xx%)	N (x.xx%)
Oral glucose lowering drugs use at index date			
Yes	N (x.xx%)	N (x.xx%)	N (x.xx%)
No	N (x.xx%)	N (x.xx%)	N (x.xx%)
Sulfonylureas use prior to index date			
Yes	N (x.xx%)	N (x.xx%)	N (x.xx%)
No	N (x.xx%)	N (x.xx%)	N (x.xx%)
Sulfonylureas use at index date			
Yes	N (x.xx%)	N (x.xx%)	N (x.xx%)
No	N (x.xx%)	N (x.xx%)	N (x.xx%)
Thiazolidinediones use prior to index date			
Yes	N (x.xx%)	N (x.xx%)	N (x.xx%)
No	N (x.xx%)	N (x.xx%)	N (x.xx%)
Thiazolidinediones use at index date			
Yes	N (x.xx%)	N (x.xx%)	N (x.xx%)
No	N (x.xx%)	N (x.xx%)	N (x.xx%)

Proprietary confidential information © 2024 Boehringer Ingelheim International GmbH or one or more of its affiliated companies

	Empagliflozin at index date	DPP-4 inhibitors at index date	[Country] Study population (Total)
	N	N	
GLP-1 use prior to index date			
Yes	N (x.xx%)	N (x.xx%)	N (x.xx%)
No	N (x.xx%)	N (x.xx%)	N (x.xx%)
GLP-1 use at index date			
Yes	N (x.xx%)	N (x.xx%)	N (x.xx%)
No	N (x.xx%)	N (x.xx%)	N (x.xx%)
History of diabetic complications prior to index date			
Yes	N (x.xx%)	N (x.xx%)	N (x.xx%)
No	N (x.xx%)	N (x.xx%)	N (x.xx%)
History of diabetic retinopathy or diabetic maculopathy prior to index date			
Yes	N (x.xx%)	N (x.xx%)	N (x.xx%)
No	N (x.xx%)	N (x.xx%)	N (x.xx%)
History of diabetic nephropathy prior to index date			
Yes	N (x.xx%)	N (x.xx%)	N (x.xx%)
No	N (x.xx%)	N (x.xx%)	N (x.xx%)
History of diabetic neuropathy prior to index date			
Yes	N (x.xx%)	N (x.xx%)	N (x.xx%)
No	N (x.xx%)	N (x.xx%)	N (x.xx%)

Proprietary confidential information © 2024 Boehringer Ingelheim International GmbH or one or more of its affiliated companies

	Empagliflozin at index date	DPP-4 inhibitors at index date	[Country] Study population (Total)
	N	N	
History of Diabetic lower limb severe complications prior to index date			
Yes	N (x.xx%)	N (x.xx%)	N (x.xx%)
No	N (x.xx%)	N (x.xx%)	N (x.xx%)
History of peripheral vascular disease prior to index date			
Yes	N (x.xx%)	N (x.xx%)	N (x.xx%)
No	N (x.xx%)	N (x.xx%)	N (x.xx%)
History of kidney or genitourinary stones prior to index date			
Yes	N (x.xx%)	N (x.xx%)	N (x.xx%)
No	N (x.xx%)	N (x.xx%)	N (x.xx%)
History of UTI or pyelonephritis prior to index date			
Yes	N (x.xx%)	N (x.xx%)	N (x.xx%)
No	N (x.xx%)	N (x.xx%)	N (x.xx%)
History of liver disease prior to index date			
Yes	N (x.xx%)	N (x.xx%)	N (x.xx%)
No	N (x.xx%)	N (x.xx%)	N (x.xx%)
History of pancreatitis prior to index date			

Proprietary confidential information © 2024 Boehringer Ingelheim International GmbH or one or more of its affiliated companies

	Empagliflozin at index date	DPP-4 inhibitors at index date	[Country] Study population (Total)
	N	N	
Yes	N (x.xx%)	N (x.xx%)	N (x.xx%)
No	N (x.xx%)	N (x.xx%)	N (x.xx%)
History of congestive heart failure prior to index date			
Yes	N (x.xx%)	N (x.xx%)	N (x.xx%)
No	N (x.xx%)	N (x.xx%)	N (x.xx%)
History of hypertension prior to index date			
Yes	N (x.xx%)	N (x.xx%)	N (x.xx%)
No	N (x.xx%)	N (x.xx%)	N (x.xx%)
History of stroke prior to index date			
Yes	N (x.xx%)	N (x.xx%)	N (x.xx%)
No	N (x.xx%)	N (x.xx%)	N (x.xx%)
History of myocardial infarction prior to index date			
Yes	N (x.xx%)	N (x.xx%)	N (x.xx%)
No	N (x.xx%)	N (x.xx%)	N (x.xx%)
History of autoimmune disease prior to index date			
Yes	N (x.xx%)	N (x.xx%)	N (x.xx%)
No	N (x.xx%)	N (x.xx%)	N (x.xx%)
History of COPD prior to index date			
Yes	N (x.xx%)	N (x.xx%)	N (x.xx%)

Proprietary confidential information © 2024 Boehringer Ingelheim International GmbH or one or more of its affiliated companies

	Empagliflozin at index date	DPP-4 inhibitors at index date	[Country] Study population (Total)
	N	N	
No	N (x.xx%)	N (x.xx%)	N (x.xx%)
Any ICU admission prior to index date			
Yes	N (x.xx%)	N (x.xx%)	N (x.xx%)
No	N (x.xx%)	N (x.xx%)	N (x.xx%)
Antihypertensives/ diuretics use prior to index date			
Yes	N (x.xx%)	N (x.xx%)	N (x.xx%)
No	N (x.xx%)	N (x.xx%)	N (x.xx%)
NSAIDs use prior to index date			
Yes	N (x.xx%)	N (x.xx%)	N (x.xx%)
No	N (x.xx%)	N (x.xx%)	N (x.xx%)
Oral steroids use prior to index date			
Yes	N (x.xx%)	N (x.xx%)	N (x.xx%)
No	N (x.xx%)	N (x.xx%)	N (x.xx%)
Statins/fibrates use prior to index date			
Yes	N (x.xx%)	N (x.xx%)	N (x.xx%)
No	N (x.xx%)	N (x.xx%)	N (x.xx%)
Lipid modifying agents use prior to index date			
Yes	N (x.xx%)	N (x.xx%)	N (x.xx%)

Proprietary confidential information © 2024 Boehringer Ingelheim International GmbH or one or more of its affiliated companies

	Empagliflozin at index date	DPP-4 inhibitors at index date	[Country] Study population (Total)
	N	N	
No	N (x.xx%)	N (x.xx%)	N (x.xx%)
Zoledronic acid use prior to index date			
Yes	N (x.xx%)	N (x.xx%)	N (x.xx%)
No	N (x.xx%)	N (x.xx%)	N (x.xx%)
Antibiotic use prior to index date			
Yes	N (x.xx%)	N (x.xx%)	N (x.xx%)
No	N (x.xx%)	N (x.xx%)	N (x.xx%)
BMI (closest value prior to index date)			
<20	N (x.xx%)	N (x.xx%)	N (x.xx%)
20-24.9	N (x.xx%)	N (x.xx%)	N (x.xx%)
25-29.9	N (x.xx%)	N (x.xx%)	N (x.xx%)
>30	N (x.xx%)	N (x.xx%)	N (x.xx%)
Range (min,max)	(min, max)	(min, max)	(min, max)
mean (± sd)	mean (± sd)	mean (± sd)	mean (± sd)
median (Q1,Q3)	median (Q1,Q3)	median (Q1,Q3)	median (Q1,Q3)
Smoking status (closest value prior to index date)			
Yes	N (x.xx%)	N (x.xx%)	N (x.xx%)
No	N (x.xx%)	N (x.xx%)	N (x.xx%)
Alcohol use (closest value prior to index date)			

Proprietary confidential information © 2024 Boehringer Ingelheim International GmbH or one or more of its affiliated companies

	Empagliflozin at index date	DPP-4 inhibitors at index date	[Country] Study population (Total)
	N	N	
Yes	N (x.xx%)	N (x.xx%)	N (x.xx%)
No	N (x.xx%)	N (x.xx%)	N (x.xx%)
HbA1c in mmol/mol(closest value prior to index date)			
< 48 (6.5%) mmol/mol	N (x.xx%)	N (x.xx%)	N (x.xx%)
≥ 48 (6.5 %) - <64 mol/mol (8 %)	N (x.xx%)	N (x.xx%)	N (x.xx%)
≥ 64 mmol/mol (8 %)	N (x.xx%)	N (x.xx%)	N (x.xx%)
Range (min,max)	(min, max)	(min, max)	(min, max)
mean (± sd)	mean (± sd)	mean (± sd)	mean (± sd)
median (Q1,Q3)	median (Q1,Q3)	median (Q1,Q3)	median (Q1,Q3)
eGFR in (mL/min/1.73 m²)			
<15 (ml/min/1.73 m ²) (kidney failure)	N (x.xx%)	N (x.xx%)	N (x.xx%)
15-29 (ml/min/1.73 m ²) (severely decreased)	N (x.xx%)	N (x.xx%)	N (x.xx%)
30-44 (ml/min/1.73 m ²) (Moderately to severely decreased)	N (x.xx%)	N (x.xx%)	N (x.xx%)
45-59 (ml/min/1.73 m ²) (Mildly to moderately decreased)	N (x.xx%)	N (x.xx%)	N (x.xx%)
60-89 (ml/min/1.73 m ²) (Mildly decreased)	N (x.xx%)	N (x.xx%)	N (x.xx%)
≥90 (ml/min/1.73 m ²) (Normal)	N (x.xx%)	N (x.xx%)	N (x.xx%)
Range (min,max)	(min, max)	(min, max)	(min, max)

Proprietary confidential information © 2024 Boehringer Ingelheim International GmbH or one or more of its affiliated companies

	Empagliflozin at index date	DPP-4 inhibitors at index date	[Country] Study population (Total)
	N	N	
mean (± sd)	mean (± sd)	mean (± sd)	mean (± sd)
median (Q1,Q3)	median (Q1,Q3)	median (Q1,Q3)	median (Q1,Q3)
Renal impairment			
Yes	N (x.xx%)	N (x.xx%)	N (x.xx%)
No	N (x.xx%)	N (x.xx%)	N (x.xx%)
Systolic blood pressure			
< 120	N (x.xx%)	N (x.xx%)	N (x.xx%)
≥120-<139	N (x.xx%)	N (x.xx%)	N (x.xx%)
≥140-<159	N (x.xx%)	N (x.xx%)	N (x.xx%)
≥160	N (x.xx%)	N (x.xx%)	N (x.xx%)
Range (min,max)	(min, max)	(min, max)	(min, max)
mean (± sd)	mean (± sd)	mean (± sd)	mean (± sd)
median (Q1,Q3)	median (Q1,Q3)	median (Q1,Q3)	median (Q1,Q3)
Diastolic blood pressure			
< 80	N (x.xx%)	N (x.xx%)	N (x.xx%)
80-89	N (x.xx%)	N (x.xx%)	N (x.xx%)
90-99	N (x.xx%)	N (x.xx%)	N (x.xx%)
100 or higher	N (x.xx%)	N (x.xx%)	N (x.xx%)
Range (min,max)	(min, max)	(min, max)	(min, max)
mean (± sd)	mean (± sd)	mean (± sd)	mean (± sd)

Proprietary confidential information © 2024 Boehringer Ingelheim International GmbH or one or more of its affiliated companies

Empagliflozin at index date	DPP-4 inhibitors at index date	[Country] Study population (Total)
N	N	
median (Q1,Q3)	median (Q1,Q3)	median (Q1,Q3)

Proprietary confidential information © 2024 Boehringer Ingelheim International GmbH or one or more of its affiliated companies

Table 18 Covariate balance assessment [before/after] matching comparing empagliflozin group to DPP-4 inhibitors group – [Study country].

	Empagliflozin users at index date [before/after] matching	DPP-4 inhibitors users at index date [before/after] matching	P-Value	Standardized differences
	N	N		
Age at index (years)				
18-49	N (x.xx%)	N (x.xx%)	χ^2 test p-value	std diff
50-64	N (x.xx%)	N (x.xx%)	χ^2 test p-value	std diff
65-69	N (x.xx%)	N (x.xx%)	χ^2 test p-value	std diff
70-74	N (x.xx%)	N (x.xx%)	χ^2 test p-value	std diff
75-79	N (x.xx%)	N (x.xx%)	χ^2 test p-value	std diff
80-84	N (x.xx%)	N (x.xx%)	χ^2 test p-value	std diff
85 and over	N (x.xx%)	N (x.xx%)	χ^2 test p-value	std diff
Range (min,max)	(min, max)	(min, max)		
mean (\pm sd)	mean (\pm sd)	mean (\pm sd)	t-test p-value	std diff
median (Q1,Q3)	median (Q1,Q3)	median (Q1,Q3)		
Sex				
Male	N (x.xx%)	N (x.xx%)	χ^2 test p-value	std diff
Female	N (x.xx%)	N (x.xx%)		
Highest level of education				
Compulsory	N (x.xx%)	N (x.xx%)	χ^2 test p-value	std diff
Upper secondary	N (x.xx%)	N (x.xx%)	χ^2 test p-value	std diff
Post secondary	N (x.xx%)	N (x.xx%)	χ^2 test p-value	std diff
Disposable income, individual				
< Q1	N (x.xx%)	N (x.xx%)	χ^2 test p-value	std diff

Proprietary confidential information © 2024 Boehringer Ingelheim International GmbH or one or more of its affiliated companies

	Empagliflozin users at index date [before/after] matching	DPP-4 inhibitors users at index date [before/after] matching	P-Value	Standardized differences
	N	N		
Q1 – Q2	N (x.xx%)	N (x.xx%)	χ^2 test p-value	std diff
Q2 – Q3	N (x.xx%)	N (x.xx%)	χ^2 test p-value	std diff
\geq Q3	N (x.xx%)	N (x.xx%)	χ^2 test p-value	std diff
Range (min,max)	(min, max)	(min, max)		
mean (\pm sd)	mean (\pm sd)	mean (\pm sd)	t-test p-value	std diff
median (Q1,Q3)	median (Q1,Q3)	median (Q1,Q3)		
Disposable income, family				
< Q1	N (x.xx%)	N (x.xx%)	χ^2 test p-value	std diff
